1.2 Quantitative Analysis Plan

The primary hypothesis is that receipt of YMHP (regardless of delivery format) will be associated with greater improvements in sexual health management (as measured by decreased STIs, CAS and increased PrEP uptake/adherence) as well as greater reductions in substance use, compared with youth who receive the standard of care (individual HIV testing) only. Our secondary hypothesis is that youth who elect to receive YMHP remotely will report more barriers to accessing health care compared to those who elect to receive the intervention in clinic. In addition, we hypothesize that remote-based YMHP will demonstrate greater improvements in sexual health management (as measured by decreased STIs, CAS, and increased PrEP uptake/adherence) as well as reductions in substance use, compared to clinic-based YMHP, among YMSM who do report barriers to health care access. In contrast, it is hypothesized that clinic-based YMHP will demonstrate greater improvements in sexual health management and reduced substance use among YMSM who do not report barriers to health care access. Self-management model analysis is described in the AC.

The AC will test the effect of clinic-based versus remote delivery on STI rates, alcohol and drug use behavior, CAS, and PrEP uptake through multi-level growth mixture modeling (GMM). A separate model will be run for each outcome. Each model will be a 2-level model in which individuals (Level I) are nested in clinics (Level II). This approach controls for the non-independence of individuals within clinics. Because three SRVs provide extremely limited predictive power at Level II, no site covariates are included in the model. (The models are empty at Level II).

In a GMM, a latent growth curve with an intercept and linear slope factor is specified. Latent class analysis is applied to these 2 growth components (intercept and slope) to identify groups of individuals who share trajectories. For example, with regard to drug or alcohol use, “immediate and sustained responders” may have the lowest post-intervention intercept and a flat slope. Meanwhile, “non-responders” might have the highest post-intervention intercept and a flat slope. In contrast, “delayed responders” might have a high post-intervention intercept but a significant negative slope, indicating reductions in missed medication over the follow up period.

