If modeling results indicate that discrete classes are not present, we will proceed with analyses in which the growth factors (intercept and slope) are predicted directly by intervention condition (and demographic factors found to be associated with condition after randomization or with attrition over follow up). GMMs can subsequently incorporate predictors of class membership. These analyses can be conceptualized as a multi-nominal logistic regression with the latent trajectory-class membership constituting the outcome. The predictors

of primary interest will be intervention condition, the presence of any barriers to health care access, and the interaction between condition and barriers to access. We will include as covariates any demographic variables that were associated with condition after randomization or with attrition over the follow up period.

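### SAP 1.2 does not specify the STI growth mixture model closely enough to show that it is identified on the few STI tests scheduled, and does not fix the adjustment covariates in advance

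*SAP*

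**What the plan says.** **The model.** SAP 1.2 lists STI, alcohol and drug use, condomless anal sex (CAS) and PrEP uptake, and states that "A separate model will be run for each outcome". Each model has an intercept and a linear slope, and "Latent class analysis is applied to these 2 growth components (intercept and slope) to identify groups of individuals who share trajectories". Waves, time scores, within-class variances and the rule for choosing the number of classes are not given. The only hint on timing is the drug and alcohol example, where one class "may have the lowest post-intervention intercept and a flat slope" and another "might have the highest post-intervention intercept and a flat slope".

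**The fallback.** If discrete classes are not found, "the growth factors (intercept and slope) are predicted directly by intervention condition", plus demographic factors associated with condition or attrition. Otherwise "GMMs can subsequently incorporate predictors of class membership", and there the predictors "of primary interest will be intervention condition, the presence of any barriers to health care access" and their interaction.

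**Covariates.** On clinics, SAP 1.2 says: "Because three SRVs provide extremely limited predictive power at Level II, no site covariates are included in the model". SAP 1.2.2 stratifies randomization by city and by barriers to access. It also allows adjustment for behavioural or biological baseline predictors, but only where attrition differs. SAP 1.2.3 tests baseline outcomes for imbalance, but carries only demographic factors forward.

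**The STI tests.** Protocol 6.0 schedules them at baseline and at the 3- and 9-month follow-ups (3M, 9M). The immediate post-test and 6-month visits are questionnaire only. A missed 3M or 9M test is to be made up at the next assessment. The COVID-19 modifications reduce 3M and 9M to the questionnaire, although other parts of Protocol 6.0 allow mailed kits.

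**The concern.** A model with a latent intercept, a latent slope and latent classes needs several repeated measures. Two yes/no results per person are very few. If the model is not identified, different parameter values fit the data equally well, and the software stops or returns an answer that depends on starting values. The analyst must then choose waves, constraints or number of classes after seeing which version converges. STI is one of the measures in the primary hypothesis, so these choices should not be made with the results in hand.

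The covariate rule has a similar weakness. The adjustment set is unknown until the data are seen. It need not contain the variables with the best prior claim to be there: the baseline value of the outcome and the two stratification factors.

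**Working it through.** **The plan's own STI figure.** SAP 1.2.1 gives power .80 at N = 270 for an odds ratio of .20 to .50, at prevalence .05 to .15 and ρ .2 to .5. The number of repeated measures M is not stated. I assumed a two-sided 5% test, 135 per arm, and SE² = [(1+(M−1)ρ)/M] × 2/[n p̄(1−p̄)] on the logit scale. The detectable odds ratio is then .17 to .43 for M = 2, .20 to .48 for M = 3 and .21 to .51 for M = 4. The figure cannot be reproduced without M and does not settle which waves the model uses. Nothing below rests on it.

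**Identification: inputs.** Assumption: the samples taken at one visit are combined into one yes/no result. Times in years from baseline are 0 (baseline), .5 (3M), .75 (6M) and 1.0 (9M), because the follow-ups count from the immediate post-test at 3 months. Free proportions per group: 2² − 1 = 3 for two tests and 2³ − 1 = 7 for three. Parameters:

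- full two-class: 4 means + 2 variances + 1 covariance + 1 class share = 8
- two-class without within-class variance: 4 + 1 = 5
- fallback, both growth factors random: 2 means + 2 variances + 1 covariance + 2 condition effects = 7, fitted to two arms
- fallback with slope variance zero: 2 + 1 + 2 = 5

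The numerical Jacobian of the cell probabilities (logistic-normal model, Gauss-Hermite quadrature) gives the rank, which is the number of parameter combinations the data can determine. A model is identified if rank equals parameters.

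| Tests used | Full two-class | Two-class, no within-class variance | Fallback |
|---|---|---|---|
| 3M + 9M | 3/8 | 3/5 | 6/7 (5/5 with slope variance zero) |
| 3M + 9M, some made up at 6M | 5/8 | 5/5 (4/5 if both classes are flat) | 7/7 |
| Baseline + 3M + 9M | 7/8 | 5/5 | 7/7 |
| Baseline + 3M + 9M, some made up at 6M | 8/8, weakly | 5/5 | 7/7 |

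**How weak.** Take no baseline wave, N = 270, prevalence .15, ρ .2 to .5 and an assumed 10–30% of 3M tests made up at 6M. The standard error of the logit class share is then 4.2 to 54. Even at 4.2 the 95% half-width is 1.96 × 4.2 = 8.2 logits, so for a true share of .21 to .28 the interval runs from .00 to .999. With baseline as a wave the standard error is 0.19 to 0.63.

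**A visit after 9M.** Protocol 9.0 ends at 9M. Protocol 1.0 gives 15 months for participants before 10/15/19. Protocol 6.0 speaks of four further follow-ups, up to 12 months after the immediate post-test, but lists three. If a 12-month visit exists and takes make-up tests, there are four single-visit proportions and four pairs, 8 in all. The full two-class model then reaches 8/8, again weakly (smallest singular value under 0.1% of the largest).

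**Baseline adjustment, linear scale.** With unit variances and common correlation ρ, the mean of two follow-ups has variance (1+ρ)/2. After adjustment for baseline this is (1+ρ)/2 − ρ².

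- ρ = .2: .60 falls to .56, a reduction of .04/.60 = 6.7%
- ρ = .5: .75 falls to .50, a reduction of .25/.75 = 33.3%

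**The same step for the STI odds ratio.** In a simulated logistic fit under no effect, with prevalence near .15, adding baseline STI raised the variance of the log odds ratio by about 1% at ρ = .2 and 18–19% at ρ = .5. The conditional odds ratio also lies further from 1, so this is not a loss of power, but the linear-scale gain does not carry over.

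**The case against.** **The plan never excludes baseline as a wave.** This stands. The post-intervention intercept appears only in a drug and alcohol example. With baseline included, the restricted two-class model and the fallback are both identified.

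**Predictors can identify the classes.** This is partly right. If condition, barriers and their interaction enter together with the classes, the restricted two-class model on 3M + 9M has rank 8 of 8 when one main effect on class is non-zero, but 6 of 8 when none is. Identification would then depend on the effect under test, and SAP 1.2 adds predictors after the classes are formed.

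**There is a fallback.** It is triggered by finding no discrete classes, which 3M + 9M cannot show for STI.

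**City is already in the model.** Clinics do form Level II, and SAP 1.2.1 cites earlier network trials with no significant variation between sites. So city is not ignored. The point is only that a stratification factor with three levels is better handled by two fixed terms than by an empty level with three units.

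**Stronger readings.** A reader might infer that STI cannot be analysed, that all outcomes are affected, or that COVID removed the tests. The documents support none of these. Some versions are identified, the self-report outcomes have four post-baseline questionnaires, and mailed kits were available. A reader might also infer a 7–33% precision loss for STI, which the calculation above contradicts.

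**Conclusion.** The concern holds as a gap in specification. With one yes/no result per visit and no baseline wave, neither two-class form is identified on the scheduled tests (3/8, 3/5), nor is the fallback with both growth factors random (6/7). With baseline as a wave only the full two-class model fails (7/8). Make-up tests identify some versions, but without a baseline wave they say almost nothing about class size. How far they help depends on whether a visit after 9M exists, and Protocol 1.0 and 6.0 must be reconciled with 9.0 on this. These ranks do not depend on whether N is 270 (Protocol 2.0 and 12.0, SAP 1.2.1) or 180 (Protocol 1.0, and 60 per site in 25.0).

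The covariate point holds on the text alone. The baseline outcome is never a fixed covariate, city enters only as the empty Level II, and the fallback's predictor list omits barriers and their interaction with condition. The 7–33% variance reduction illustrates continuous or count outcomes only, relative to an analysis that does not use baseline. No precision gain is claimed for STI, no figure is given for city, and no power loss is claimed for the SAP's own model. This should be corrected; confidence is medium, because the key modelling choices are unstated.

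**What to change.** 1. **STI.** Pre-specify one marginal logistic model (GEE, participant as cluster, small-sample standard errors) of the 3M and 9M results on condition and visit. Always adjust for baseline STI, city (two fixed terms) and barriers. Keep a pre-specified condition-by-barriers term for the moderation hypothesis. Define condition for each hypothesis, because SAP 1.2 hypothesises YMHP against standard of care but its model sentence compares clinic with remote delivery. State how the samples of a visit form one result, count a make-up test towards the visit it replaces, and impute missing results under missing at random, in line with SAP 1.1.
2. **CAS, drinking and drug use.** State whether baseline is a growth wave. If not, always include the baseline value; if so, do not add it again. Always include city, barriers and the interaction, in the fallback too.
3. **PrEP uptake.** Always include city, barriers and the interaction. A baseline value would be nearly constant, because Protocol 10.0 excludes current users of Truvada as PrEP.
4. **Selection.** Drop the choice of covariates by observed baseline imbalance.
5. **Growth models kept.** State waves, time coding, variance constraints and the class-selection criterion.

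**Cost.** SAP wording and modest programming; baseline STI, city and barriers are already collected. STI loses its trajectory classes, gets an odds ratio conditional on covariates, and needs the imputation step.

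**Small samples.** At prevalence .05 only about 18 (N = 180) or 27 (N = 270) results would be positive. In 2,000 simulated null trials per setting, a Firth-penalised fit with Mancl-DeRouen standard errors kept type I error at .039–.060. With plain robust errors it reached .100, and an unpenalised fit failed in up to 4.8% of trials. These simulations had no missing data, so the imputation step is untested.

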
1.2.2 Equivalency Checks

The AC will ensure that randomization is stratified by city and the presence of any barriers to healthcare access. Further, they will monitor randomization to ensure that condition is not associated with characteristics that would require adjustment in proposed analyses. To assess differential attrition, we will utilize a multilevel modeling approach (to account for the nesting of participants within clinic/city) to assess for condition, time, and condition \times time interaction effects in the proportion of completed assessments across the length of follow-up. Any evidence of differential attrition will be examined to determine whether there are baseline demographics, behavioral, or biological predictors that are associated with such differences in attrition. These effects will be adjusted for in subsequent analyses.

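### The barriers-moderation hypothesis has no specified test for any outcome in which no latent classes are found

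*SAP*

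**What the plan says.** SAP 1.2 and Protocol 2.0 state the same moderation hypothesis in two halves. Remote delivery is expected to do better "compared to clinic-based YMHP, among YMSM who do report barriers to health care access". In the other half, "clinic-based YMHP will demonstrate greater improvements in sexual health management and reduced substance use among YMSM who do not report barriers".

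The analysis in SAP 1.2 has two branches, chosen separately for each outcome because each outcome has its own model.

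- **No classes.** "If modeling results indicate that discrete classes are not present", then "we will proceed with analyses in which the growth factors (intercept and slope) are predicted directly by intervention condition (and demographic factors". The demographic factors are those related to condition after randomisation or to loss to follow-up.
- **Classes found.** A multinomial regression of class membership, in which the main predictors are condition, "the presence of any barriers to health care access, and the interaction between condition and barriers to access".

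Two other places show that moderation is a planned question. SAP 1.2.2 says that "randomization is stratified by city and the presence of any barriers to healthcare access". SAP 1.2.1 closes its power analysis with a statement that 270 participants suffice for a moderation effect of f-squared .02.

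**The concern.** The interaction that would answer the hypothesis sits in only one of the two branches. If an outcome shows a single trajectory class, the analyst who follows the SAP fits condition and demographics, and the moderation question gets no answer for that outcome. Because the branch is picked outcome by outcome, moderation could be tested for heavy drinking and left untested for STIs, purely as a by-product of how many classes each model retained. Any interaction added to the fallback at that stage would be a post hoc choice, made after the trajectories had been seen.

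**Working it through.** **1. Does the class branch still supply a test when there is one class?** A multinomial regression on K classes has K − 1 equations. With K = 1 that is 0 equations, so there is no outcome left to regress and the interaction disappears with it.

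**2. Do the closing predictor sentences cover both branches?** The fallback sentence carries its own predictor list and its own covariate rule. The later sentences, which name barriers and the interaction, directly follow the description of the class-membership regression and state the covariate rule again. That repetition would be unnecessary if they governed the fallback too.

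**3. Is there a test elsewhere?**

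- SAP 1.2.2: a baseline predictor of differential attrition may be adjusted for. Barriers could enter this way as a covariate, but no interaction is named.
- SAP 1.2.3: demographic factors may be added after baseline comparisons. Again there is no interaction.
- SAP 1.2.1: the moderation power sentence is tied to no model.
- Protocol 2.0, Secondary Aim: delivery format is to be related to preference, session retention and response. Barriers are not mentioned and no model is given.
- The protocol has no statistical analysis section.

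So no moderation test is specified in the no-class branch.

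**4. What does condition mean?** The hypothesis compares remote with clinic delivery. The modelling paragraph of SAP 1.2 also speaks of clinic versus remote delivery, while the primary hypothesis just above it compares YMHP with standard of care. Under Protocol 2.0 and 6.0 (Randomization), participants are now randomised to YMHP or standard of care, and those in YMHP choose their delivery. Protocol 6.0 lets the choice differ from session to session. If condition is the randomised arm, condition-by-barriers asks whether YMHP beats control more in one barriers group than in the other, which is a different question.

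**5. The plan's moderation figure.** SAP 1.2.1 gives N = 270 and f² = .02, but no alpha or power. I assume a two-sided alpha of .05 and a 1-df F test for the added interaction, with three model terms, noncentrality λ = f² × N and N − 4 error degrees of freedom.

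- N = 270: λ = .02 × 270 = 5.4, power .64. Power of .80 needs N = 395.
- If f² refers to one assessment and four follow-ups are averaged under compound symmetry, f² becomes .02 / [(1 + 3ρ)/4]. For an assumed ρ of .2, .5 and .7 this is .050, .032 and .026, and power is .96, .83 and .75.
- Only YMHP recipients have a delivery mode. Their number is not given. Assuming half of 270, N = 135: λ = .02 × 135 = 2.7, power .37. With the same averaging it is .73, .54 and .46.

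These figures show only how the right comparison costs precision. The gap in the plan does not depend on them.

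**The case against.** The best defence is that calling barriers and the interaction predictors of primary interest shows they were meant to be in the model whichever branch is taken. The intent is plausible, and if it is right one clause settles the matter. As written, though, the fallback has a separate list that leaves them out.

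It is also fair that the hypothesis is secondary and that the primary comparison is unaffected. That limits the weight of the point but does not remove it.

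Two stronger readings should be resisted.

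- A reader might infer that the fallback is the branch to expect, so that the hypothesis will probably go untested. The documents do not support this. The outcomes are binary (STIs, PrEP uptake) or counts (drinking and drug-use days, CAS acts). SAP 1.2 states neither the outcome distributions nor the rule for deciding on classes. Normal data without classes would tend to return one class, but skewed counts from a single population can return two under a normal mixture. Which branch applies is unknown.
- A reader might infer that cutting barriers to any versus none is a flaw that wastes power. The moderation hypothesis is itself worded as reporting or not reporting barriers, and the stratifier is any/none, so that term is the direct test. The barriers instrument is not described. Only the separate hypothesis that "youth who elect to receive YMHP remotely will report more barriers to accessing health care" hints at a graded measure. A figure for lost information would have to assume both a distribution for that score and a linear effect.

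**Conclusion.** The point holds as an omission in one branch. For every outcome without discrete classes, the stated moderation hypothesis has no specified analysis. The number of outcomes affected can be anything from none to all of them. The conclusion rests on reading the SAP text as it stands, not on a simulation or a power figure.

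It would be wrong to infer that the hypothesis is safe whenever classes are found. The class-branch interaction tests it only if condition means delivery mode, which SAP 1.2 does not settle. Where participants chose their mode, even that test is a non-randomised comparison. The weight is moderate: a secondary hypothesis, a planned branch and an inexpensive repair before the data are analysed.

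**What to change.** Amend SAP 1.2 as follows.

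- State that, whichever branch is taken, one secondary model per outcome will be fitted on the growth factors (intercept and slope) with delivery mode, the any/none barriers indicator and mode-by-barriers, among YMHP recipients. Report the remote-versus-clinic difference separately for participants with and without barriers.
- Define condition for this test as delivery mode, and say how a participant whose sessions were of mixed mode is classified.
- Label the comparison non-randomised where mode was self-selected, and distinguish the subsample that Protocol 2.0 describes as randomised to a mode.
- If YMHP versus standard of care by barriers is also of interest, list it as a separate question with its own model.
- Tie the moderation sentence in SAP 1.2.1 to this model, with its alpha, its power and the number of YMHP recipients.

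A graded barriers score is at most an optional sensitivity analysis, if the instrument yields one. The cost is SAP wording and one more model per outcome, with no change to trial conduct. The price is lower precision, because participants in the standard-of-care arm have no delivery mode during follow-up and drop out of this comparison.

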Hypothesis: The primary hypothesis is that receipt of YMHP (regardless of delivery format) will be associated with greater improvements in sexual health management (as measured by decreased STIs, CAS, and increased PrEP uptake/adherence) as well as reductions in substance use, compared with youth who receive the standard of care (individual HIV testing) only.

Secondary Hypothesis: We hypothesize that youth who elect to receive YMHP remotely will report more barriers to accessing health care compared to those who elect to receive the intervention in clinic. In addition, we hypothesize that remote-based YMHP will demonstrate greater improvements in sexual health management (as measured by decreased STIs, CAS, and increased PrEP uptake/adherence) as well as reductions in substance use, compared with clinic-based YMHP, among YMSM who do report barriers to health care access. In contrast, it is hypothesized that clinic-based YMHP will demonstrate greater improvements in sexual health management and reduced substance use among YMSM who do not report barriers to health care access.

PROTOCOL TITLE: Comparative effectiveness trial of clinic-based delivery of an HIV risk reduction intervention (YMHP) for YMSM, Phase 2

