1.2.1 Power Analysis

First, we analyzed power assuming independence of participant observations (assuming that the nesting of people-within-clinic was irrelevant). With regard to STIs, we utilized the “repeated measures” module of PASS 13.0 to examine power to detect odds ratio differences in a repeated measures design. Specifying compound symmetry, we allowed ρ to vary between .2 and .5. Assuming the prevalence of STIs in the remote-based condition varies between .05 and .15, the proposed design ($N = 270$) has power .80 to detect an odds ratio of .20 to .50. Similarly, with regard to the odds of PrEP uptake, allowing the rate of uptake in the remote-based condition to vary between .05 and .20 and allowing ρ to vary between .4 and .7, the proposed design has power of .80 to detect an odds ratio of 1.9 to 2.3. With regard to number of alcohol and drug use days, we utilized the *Tests for Two Poisson Means* module in PASS 13.0. Based data from our previous studies, we allowed the rate of heavy drinking in the phone-based condition to vary between 7 and 9 days during a 30-day assessment. The study is adequately powered to detect a 3% reduction in number of heavy drinking days in the clinic-based condition at any single follow up point. Allowing the rate of drug use in the remote-based condition to vary between 3 and 5 days during a 30 day assessment period, the study is adequately powered to detect a 4% reduction in drug use in the clinic-based condition. A similar analysis was conducted with respect to CAS. Based on our previous research, we allowed the rate of CAS in the phone-based condition to vary between 2 and 4 acts in a 30 day assessment period. The study is powered to detect a difference as small as 5% between the remote and clinic-based YMHP conditions. The nesting of individuals within SRVs has the potential to reduce power because substantial variability in outcome across SRVs can obscure level II treatment effects [70, 71]. The design effect can be used to tailor power analyses calculated under assumptions of independence. In the case of a Level I predictor with a fixed effect which is uncorrelated with other covariates in the model, the design effect is equal to the $1 - \rho$, where ρ is the intra-class correlation or the percentage of variance accounted for by variability between SRVs [71]. In previous intervention trials conducted within the ATN [72], between clinic site variability in HIV related outcomes did not differ significantly from zero. Based on the characteristics of ATN clinics, we anticipate a similar absence of variability across clinics, suggesting that the design effect would result in a negligible reduction in power. Finally, a sample size of 270 is sufficient to detect a moderation effect with an f^2 of .02. Cohen [73] designates this as a small effect, however recent work has characterized an effect of this size as moderate to large as applied to moderation [74].

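### The secondary hypothesis makes two opposite claims, one per barriers group, but the SAP plans only a format-by-barriers interaction and no remote-versus-clinic estimate within either group

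*SAP*

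**What the plan says.** Protocol 2.0 (Secondary Hypothesis) and SAP 1.2 state the same two claims. Remote delivery is expected to produce larger improvements "compared to clinic-based YMHP, among YMSM who do report barriers to health care access". For the other group, "clinic-based YMHP will demonstrate greater improvements in sexual health management and reduced substance use among YMSM who do not report barriers" to care.

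SAP 1.2 then describes the growth mixture model. Its predictors of main interest are intervention condition, "the presence of any barriers to health care access, and the interaction between condition and barriers to access". If no latent classes are found, the fallback is a model in which "the growth factors (intercept and slope) are predicted directly by intervention condition", together with selected demographic factors. Neither barriers nor the interaction is named there.

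SAP 1.2.1 gives power for the overall remote-versus-clinic difference on several outcomes, and closes by saying that "a sample size of 270 is sufficient to detect a moderation effect with an f^2 of .02". It states no alpha or power for that claim. Neither document plans a format contrast within a barriers group or says what result would count as support for either half.

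**The concern.** The hypothesis concerns the sign of the format effect in each of two groups. The null hypothesis of the interaction is that the two format effects are equal. Rejecting it says that they differ, and leaves open whether they have opposite signs, whether one is zero, or whether one format is better in both groups by different amounts. Only the first pattern is what the trial predicts.

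Protocol 3.0 (Remote Delivery) says that the way access and delivery method combine is meant to inform how clinics implement YMHP. If a significant interaction were reported as a crossover, youth without barriers could be steered to clinic delivery when remote delivery is as good or better for them. If the within-group contrasts are added only after the data are seen, the choice of contrast, scale and criterion is open across several outcomes.

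**Working it through.** **Inputs.** From SAP 1.2.1: f² = .02 and N = 270. Assumed, because the documents do not give them: two-sided alpha of 5%; a continuous outcome with SD 1; four equal cells (format by barriers). N = 135 is also shown. It is half of 270, for the case where only YMHP recipients inform the format comparison and allocation is 1:1. The stated total itself varies: 270 in Protocol 2.0, Protocol 12.0 and SAP 1.2.1, but 180 in Protocol 1.0, and 3 × 60 = 180 in Protocol 25.0.

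**Step 1. The plan's figure.** For one interaction term, noncentrality is f² × N = .02 × 270 = 5.4 with 1 and 266 degrees of freedom. Power is 63.9%. Reaching 80% would need N = 395. The SAP may have relied on unstated averaging over repeated follow-ups (four follow-ups at a within-person correlation of .5 give 83%), so its statement is not reproduced but is not shown to be wrong. The point below does not depend on it.

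**Step 2. Translate f² into format effects.** Let d₁ be remote minus clinic with barriers, d₂ the same without barriers, and I = d₁ − d₂. With equal cells, f² = I²/16, so I = √(16 × .02) = 0.566 SD.

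**Step 3. Interaction test.** SE(I) = √(4/(N/4)) = 4/√N. At N = 270 this is 0.243, so z = 0.566/0.243 = 2.32, and the probability of significance in the predicted direction is Φ(2.32 − 1.96) = 64%. Only d₁ − d₂ enters, so the answer is the same for every pattern with that difference:

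| True pattern | d₁ | d₂ | Interaction significant |
|---|---|---|---|
| Crossover, as hypothesised | +0.283 | −0.283 | 64% |
| Effect only with barriers | +0.566 | 0 | 64% |
| Effect only without barriers | 0 | −0.566 | 64% |
| Remote better in both | +0.849 | +0.283 | 64% |

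**Step 4. Sensitivity to effect size.** With d₂ = 0 and d₁ = 0.3, 0.5 or 0.8 SD, the interaction is significant in 23%, 54% or 91% of trials at N = 270, and in 14%, 31% or 64% at N = 135.

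**Step 5. What the within-group contrasts can do.** SE(d) = √(2/(N/4)).
- N = 270: SE = 0.172. For the symmetric crossover, z = 0.283/0.172 = 1.64 and power per contrast is Φ(1.64 − 1.96) = 37.6%. Both significant: 0.376² = 14%.
- N = 135: SE = 0.243, z = 1.16, power per contrast 21.2%. Both significant: 0.212² ≈ 5%.
- With one half null (0.566 and 0) at N = 270, both contrasts are significant in the predicted directions in 0.908 × 0.025 = 2.3% of trials.

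**The case against.** A reader might infer three stronger things, and the documents do not support them.

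First, that the interaction is the only format test planned or powered. It is not. SAP 1.2 says that clinic versus remote delivery will be tested on each outcome, and most of SAP 1.2.1 concerns that overall difference. The overall effect would also warn against some misreadings. If remote were better by 0.8 and 0.3 SD, the average is 0.55 SD, which is significant in 99% of trials at N = 270 and 89% at N = 135. What remains is that the overall effect tests neither half: in a symmetric crossover the two effects cancel to zero. With reference coding, the condition coefficient would be the format effect in one group, but the SAP gives no coding and does not offer it as a test.

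Second, that 54% or 64% is a false-positive rate. In each pattern above the format effects truly differ, so these figures are power. They would become errors only if a significant interaction were taken as proof of a crossover, and neither document states that rule.

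Third, that both halves must be shown together or the hypothesis fails. The two halves are stated in separate sentences and can be reported separately, so a mandatory joint rule is debatable.

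The calculation is also an approximation. The main analysis models class membership, with K − 1 interaction coefficients for K classes, and equal cells sit badly with the prediction that remote choosers report more barriers. The interaction null still concerns a difference between effects on the logit scale, so the logic carries over, but the percentages may not.

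**Conclusion.** The concern holds as a mismatch between a two-part directional hypothesis and the planned terms. The interaction answers whether the format effect differs by barriers. It does not answer whether remote is better with barriers or clinic is better without, and neither the overall format effect nor its power figures fill that gap. At f² = .02 and N = 270 the interaction is significant about 64% of the time whichever of the four patterns is true, under a normal outcome, equal cells and two-sided 5%. How often a one-group effect produces significance depends on its size, from 14% (0.3 SD, N = 135) to 91% (0.8 SD, N = 270), so no single frequency should be claimed.

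The hypothesis is secondary and the remedy is cheap, so this should be changed, but it does not threaten the primary comparison.

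**What to change.** In SAP 1.2:

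1. Keep the interaction, described as the test of moderation only.
2. Define a delivery-format term: remote versus clinic among YMHP recipients, separate from randomised YMHP versus standard of care. Protocol 6.0 (Randomization) now uses condition for the latter, and Protocol 2.0 lets participants choose their format. Label the comparison non-randomised wherever format was self-chosen.
3. Put format, barriers and their interaction into the no-class fallback model as well.
4. Pre-specify two contrasts, remote minus clinic with barriers and remote minus clinic without, each with a 95% confidence interval on the outcome scale (days, acts or risk).
5. Report each half of the hypothesis on its own contrast, and do not call the result a crossover on the interaction alone.

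In SAP 1.2.1, add that showing both halves is unlikely at the planned effect size (about 14% at N = 270 and 5% at N = 135 for a symmetric crossover).

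The cost is SAP wording, a defined format variable and two contrasts per outcome, with no new data. The price is precision: the 95% interval for a within-group contrast is about ±0.34 SD at N = 270 (1.96 × 0.172) and ±0.48 SD at N = 135 (1.96 × 0.243).
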